# 5.0 Multiple sites:

N/A

# **6.0 Incomplete Disclosure or Deception:**

N/A

### 7.0 Recruitment:

Participants will be recruited from the Departments of Internal Medicine and Pulmonary Medicine at Rush University Medical Center, under the supervision of study co-investigator [name]. The Department of Internal Medicine provides approximately 87,000 primary care visits per year at 10 sites in the medical center and community-based clinics in the Chicago area. The department sponsors more than 50 active clinical trials and interfaces with the Electronic Data Warehouse to facilitate clinic-based recruitment. We expect that 40% of patients with COPD identified through clinic-based recruitment are current cigarette smokers.

Trained study personnel will identify potential participants through reviewing Epic data requests, screening outpatient clinic schedules, and provider referral. Potentially eligible patients who are identified through chart review process will be mailed a recruitment letter to describe the research study and inform them that study staff will be calling them within the next week. Patients will have the opportunity to 'opt out' by calling the study team if they are not interested in being contacted.

Study recruitment will also be supplemented by partnerships with Rush University organizations such as the Tobacco Oversight Committee and Rush Lung Institute, and community organizations, including the Respiratory Health Association (RHA) and American Lung Association (ALA). [name] will share IRB-approved recruitment materials with these organizations through multiple communication channels (i.e., newsletters, e-newsletters, website postings) to reach potentially eligible COPD patients and providers. She and other study team members will also attend events and meetings hosted by these organizations and post sign-up sheets where interested individuals may provide their contact information. The study team will call and/ or email these individuals to describe the study and assess interest in participating and eligibility, if applicable.

### **8.0 Consent Process:**

We will obtain electronic informed consent via the REDCap e-consent template. After completing the phone screener, those who remain interested and eligible for the study will be immediately emailed or texted a link to the appropriate IRB-approved online consent form in REDCap. Study staff will discuss the consent form while on the phone with the participant following the screening process. If the participant does not have time for this discussion, a second phone call will be arranged. We will attempt to conduct the signature process in one continuous session with the participant. If this is not possible (e.g., the participant uses a cell phone as their only connected device, and is unable to simultaneously talk on the phone and view the REDCap e-consent), study staff will follow the consent process below to obtain verbal consent. Study staff will then follow up with the participant by email/text to obtain an electronically signed copy of the consent form as soon as possible after the phone call has ended.

Consenting procedures will follow Rush IRB guidance for the use of electronic informed consent to ensure best practices are followed in remotely obtaining informed consent. Study staff will first verify that: 1) the form the participant received is the currently approved version, 2) all pages of the consent were received, and 3) the participant can read all pages of the consent. Study staff will verify the identity of the participant by asking their date of birth. Study staff will then review all information in the consent form, similarly to how this discussion would be conducted in an in-person format. Participants will be provided with ample time to review the consent and ask any questions they may have. Those who remain interested will provide an online signature on the REDCap consent form. A PDF version of the consents will be emailed or texted to the participant. Informed consent will be obtained prior to any data collection or study procedures. There is no waiting period between informing the prospective subject of

their eligibility and obtaining the consent. Non-English speaking individuals, individuals under the age of 18, cognitively-impaired adults, and adults unable to consent will not be included in the current study.

### 9.0 Process to Document Consent:

Documentation of the consent process will occur within the REDCap e-consent project (i.e., eConsent form with electronic signature for each study participant, Consent Collection Form, and Consent Process Documentation Form).

## 10.0 Risks to Participants:

First, participants will be asked to report on their smoking, COPD symptoms, and symptoms of psychological disorders. As a result, they may experience discomfort or distress from providing self-report of private, potentially embarrassing information. Second, participants may experience nicotine withdrawal-related distress as a result of smoking cessation in Phases 2 and 3. Third, while we will make every effort to protect privacy and keep data confidential, a risk of potential for loss of confidentiality also exists.

## 11.0 Potential Benefits to Participants:

Participants may not directly benefit from the proposed research, but will contribute to the research literature on improving smoking cessation treatment for individuals with COPD. The risk/benefit ratio is seen as highly favorable, as the potential benefits of quitting smoking for improving COPD functioning and preventing the development of other smoking-related illnesses greatly outweigh the potential of temporary withdrawal discomfort and frustration associated with quitting.

# 12.0 Financial Compensation:

Participants will be provided with financial compensation for completing study assessments, as shown in table below. They will be paid \$10 to offset travel costs for each in-person study visit. Participants are only eligible for payment if all study procedures at a given assessment are completed. For Study Phase 3, payments will be provided in the form of a mailed check or reloadable debit card (Greenphire ClinCard). Participants will not be responsible for any costs associated with participating in the research.

Table 4. Financial Compensation per Participant by Study Phase					
	Visit Compensation	Travel Compensation	Total		
Phase 2					
Baseline assessment	\$20	\$10	\$30		
Electronic diary assessment	\$2 x up to 50 total	N/A	Up to \$100		
Treatment sessions	N/A	\$10 x 4 total	\$40		
CO assessment	\$10	N/A	\$10		
End-of-treatment assessment	\$20	\$10	\$30		
TOTAL			Up to \$210		

# 13.0 Provisions to Protect the Privacy Interests of Participants:

The risk of potential loss of confidentiality will be minimized through training and ongoing supervision of study staff as well as storage of all private health information on a secure network drive (detailed in section 14.0 below).

## 14.0 Confidentiality and Data Management:

### **Data Management**

Sources of data include a) consent forms, b) self-report questionnaires, c) expired CO values, d) digital audio recordings, and e) chart review variables. Data will be stored for a minimum of 7 years after study completion on a secure Rush University network drive and in a double-locked office suite within the Department of Preventive Medicine. At the conclusion of the study, all data will be stripped of identifiers and archived for future analysis.

Procedures to secure the data include training and ongoing supervision of study staff; use of an encrypted, digital recording device; storage of all private health information on a secure network drive; and the use of numeric code identifiers. Digital audio recordings will be identified by numeric code only, and submitted to the transcription service via their secure, cloud-based Exavault server. [name] will be responsible for data and safety monitoring activities. She will provide oversight of the maintenance of patient confidentiality and will report any breaches of confidentiality to the IRB. She will report any changes to the study's risk/benefit ratio to the IRB. Only the study investigators will have access to the master list of participants' names and codes. All co-investigators and study personnel have completed CITI training in human subjects research.

All questionnaire measures will be completed using REDCap data management software, which allows real-time data quality control measures (e.g., requiring fields to be completed, restricting ranges of acceptable values). We will also complete data quality checks by automatically setting each form status to 'Unverified' upon initial entry. Study staff will click on each unverified record, check for data quality and completeness, and select either 'Complete' or 'Incomplete.' They will then lock the form to prevent further changes, with administrative privileges set to unlock forms only for the study investigators. REDCap data will be downloaded and backed up on the secure Rush University network drive on an ongoing, monthly basis.

#### **Data Analyses**

Phase 2 Data Analyses. We will examine change scores in the behavioral target over the course of treatment (i.e., with visual interpretation and calculation of non-overlapping parameters) and rates of achieving 24-hour abstinence by treatment module. Only those treatment components that demonstrate effects as specified in the hypothesized pathway on both milestones across participants will be included in a finalized treatment manual for use in Phase 3. We will secondarily examine magnitude of effect size for each treatment component on the behavioral target, relative to baseline, with Shadish's d, a measure of effect size specifically for single-case designs and equivalent to Cohen's d. If all effect sizes are medium or greater (≥ 0.5), we will include all 3 components in the multi-component treatment in Phase 3; otherwise, we will select the two components with the highest effect sizes.

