Component 1: Mindfulness. This module introduces mindfulness training skills, with the goal of cultivating nonjudgmental, present-focused experience of emotions, thoughts, and physical sensations related to cigarette smoking. By progressing though a series of experiential exercises (e.g., awareness of the breath, anchoring in the present), this module seeks to reduce maladaptive attempts to control negative emotions and facilitate tolerance of the physical and emotional symptoms of nicotine withdrawal.

Component 2: Interoceptive Exposure (Practice Quitting). This module introduces interoceptive exposure, a technique in which participants purposefully and systematically complete exercises to evoke physical sensations typically associated with anxiety and distress, in order to reduce fear and avoidance of these sensations. Interoceptive exercises will focus on a gradual exposure to nicotine withdrawal symptoms, through a series of 'practice quit attempts' (i.e., brief periods of smoking abstinence without intention to permanently quit).

Component 3: Behavioral Activation (Countering Emotional Behaviors). Lastly, this module introduces behavioral activation, which seeks to increase positive emotions by systematically introducing greater

engagement with natural rewards. Treatment sessions focus on the identification of avoidance strategies, including cigarette smoking as a coping strategy for negative emotions. The goal of this treatment module is to replace smoking with adaptive coping strategies to facilitate contact with and enjoyment of reinforcing activities that are incompatible with smoking.

Treatment Fidelity. All treatment sessions will be delivered by trained study counselors, supervised by the PI, a licensed clinical psychologist. [name] has extensive experience in cognitive-behavioral therapy for mood and anxiety disorders, as well as behavioral counseling for smoking cessation. She obtained specialized training in delivery of the proposed intervention at the Unified Protocol Institute at Boston University in October, 2017. Sessions will be audio recorded, with 20% of sessions reviewed by an independent evaluator using standardized fidelity ratings for each UP module.

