COPD-Related Measures			
Six-minute walk test	X		
Spirometry (FEV1)	X		
Charlson Comorbidity Index	X		
COPD Assessment Test	X		X
PROMIS- Dyspnea Task Avoidance	X		X
PROMIS- Dyspnea Emotional Response	X		X
Depression and Anxiety Measures			
PROMIS- Depression short form	X		X
PROMIS- Anxiety short form	X		X
Treatment-Related Measures			
Freiberg Mindfulness Inventory	X	X	X
Avoidance and Inflexibility Scale	X	X	X
Behavioral Activation for Depression			
Scale	X	X	X

Depression and Anxiety Symptoms. PROMIS short forms will be used to assess past-7 day depression and anxiety symptoms. 

Treatment Implementation. To assess treatment implementation, participants will complete process measures at each treatment session assessing skill acquisition specific to each module (i.e., Freiberg Mindfulness Inventory,  Avoidance and Inflexibility Scale,  and Behavioral Activation for Depression Scale,  respectively).

Behavioral Target. The behavioral target will be smoking for affect regulation, as measured by 13 items from the Smoking Motives Questionnaire-Revised (SMQ-R).  $^{33,60}$  Items are adapted from a measure of drinking motives and have been validated to assess coping motives across classes of substance use.  $^{32,60,61}$  SMQ-R items can be modified to assess within-subject, state-like motives for use via ecological momentary assessment  $^{62}$  and have demonstrated good internal consistency.  $^{63}$  Further, these items are sensitive to treatment-related change (i.e., reduced as a function of a brief behavioral intervention) $^{64,65}$  and specifically related to reductions in substance use and associated problems, above and beyond non-affective motives.  $^{64,65}$  Responses are scored from 0 (not at all) to 100 (extremely) and averaged to index the overall tendency to smoke for affect regulation. Threshold of clinically-significant change is set at  $\geq 30\%$ , as this change magnitude was associated with substance use outcomes in prior studies.  $^{64,65}$  Specific items which index smoking for distress termination (e.g., "To turn off negative thoughts about myself"), anxiety reduction (e.g., "Because it helped me when I was feeling nervous"), and pleasure enhancement motives (e.g., "To help me feel more positive about things in my life") will be examined separately in follow-up exploratory analyses.

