Clinical Endpoint. The clinical endpoint will be achievement of 24-hour smoking abstinence at end-of-treatment, as verified by CO < 5 ppm,  $^{66,67}$  for at least 60% of participants (i.e., 3 of the 5 participants receiving each module), as this is consistent with rates of initial abstinence achieved by established smoking cessation treatments.  $^{68,69}$  We chose this endpoint because it is highly sensitive to treatment effects,  $^{70}$  strongly predictive of long-term abstinence,  $^{69,71}$  and especially relevant for smokers with elevated psychological risk factors who are vulnerable to early lapse.  $^{72,73}$ 

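### Do the unwritten rules for smoke-free diary nights, and for how many participants must reach 30%, undermine the choice of modules for Phase 3?

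*Combined protocol and SAP*

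**What the plan says.** The behavioral target (section 4.0, Measures, Behavioral Target) uses 13 items from the Smoking Motives Questionnaire-Revised (SMQ-R): "Responses are scored from 0 (not at all) to 100 (extremely) and averaged to index the overall tendency to smoke for affect regulation". The items ask about reasons for smoking, for example "Because it helped me when I was feeling nervous". The plan then says "Threshold of clinically-significant change is set at" 30% or more, and ties no number of participants to it. Aim 2 in section 1.0 gives the 30% in the same way.

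The other milestone, 24-hour abstinence verified by CO (Clinical Endpoint), does have a count: 60%, that is "3 of the 5 participants receiving each module".

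Among the three modules, only Interoceptive Exposure has practice quit attempts before the quit date, described as "brief periods of smoking abstinence without intention to permanently quit". Their number and length are not given.

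Section 14.0 (Data Analyses) starts from visual interpretation and non-overlap parameters for the target, together with abstinence rates by module, and requires both milestones: only modules that "demonstrate effects as specified in the hypothesized pathway on both milestones across participants will be included in a finalized treatment manual". It then turns, secondarily, to a standardized effect size d for single-case designs. If all three values are at least 0.5, all three modules are kept; "otherwise, we will select the two components with the highest effect sizes". The hypothesized pathway to which the milestone rule refers is in Figure 3, which is not visible in the text reviewed.

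**The concern.** A question about why one smoked has no natural answer on a day without smoking. Section 14.0 (Data Management) says that REDCap allows "requiring fields to be completed, restricting ranges of acceptable values". If the diary items are required, a smoke-free night will tend to be entered as 0. Practice abstinence belongs to one module only, so that module's exercise could be counted as its effect. This would be a systematic tilt, which more participants would not remove.

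The missing count adds a second freedom. The 30% milestone could be read as a module mean, as 3 of 5 or as all 5, and the choice could be made after the data are seen. At stake is which modules enter Phase 3, and whether a weaker module displaces a better one when only two are kept.

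There is also a mismatch on the same measure. The End-of-Treatment Session text says the behavioral target is assessed at that visit, while Table 2 marks the SMQ-R at baseline only.

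**Working it through.** **1. The plan's own figures.** 15 participants / 3 modules = 5 per module, and 3/5 = 60%, as stated. For the diaries, baseline is 7 or 21 nights, the first to the fourth weekly session spans 21 days, and the quit day adds 1. So 7 + 21 + 1 = 29 and 21 + 21 + 1 = 43, as stated. Treatment-phase nights are 29 − 7 = 43 − 21 = 22. The last of these is the quit day, which may be smoke-free in any module.

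**2. Zeros alone.** If k of 22 nights are scored 0 and nothing else changes, the mean falls by k/22.

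| k | apparent reduction |
|---|---|
| 0 | 0% |
| 1 | 4.5% |
| 2 | 9.1% |
| 3 | 13.6% |
| 6 | 27.3% |
| 7 | 31.8% |

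Zeros alone need 7 of 22 nights to reach 30%. With k = 3, the real reduction r that reads as 30% solves (1 − r) × 19/22 = 0.70, so r = 1 − 0.70/(19/22) = 18.9%.

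**3. Effect on the 30% milestone, read as 3 of 5 on nightly means.** All inputs here are assumptions: mean score 60, SD 20, half of the variance between persons, autocorrelation 0.3, SD of personal reduction 10 percentage points, and a true reduction of 25% on smoking nights.

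- Smoke-free nights left out: a module passes in about 24% of simulations.
- Scored 0, with every participant having exactly k such nights: about 40%, 60% and 78% for k = 1, 2, 3.
- Three planned nights, each achieved independently with probability 50% or 30%: about 50% or 38–39%.
- k = 3, but medians in place of means: 48%.
- k = 3 and no true effect: about 1%.
- Non-overlap of all pairs, one of the non-overlap measures: about 0.76 at k = 0 and 0.79 at k = 3.

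The 78% therefore needs full adherence, whole smoke-free days, zero scoring and a nightly mean, all at once.

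**4. Effect on d.** The exact form of d comes from a cited source outside the documents, so the form used here is assumed. With a true d of 0.4 in all three modules, Interoceptive Exposure reads 0.50, 0.57 and 0.64 for k = 1, 2, 3 instead of 0.41 to 0.42. The d rule alone then keeps it in 82%, 91% and 95% of trials instead of 66% to 67%. These are not selection probabilities under the plan, because they omit the two milestones. CO-verified abstinence is one of them, and diary scoring cannot alter it.

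**5. Effect of the count.** Readings can conflict. Reductions of 90, 30, 15, 10 and 10% average 155/5 = 31% with 2 of 5 at 30%. Reductions of 32, 31, 30, 0 and 0% average 93/5 = 18.6% with 3 of 5. Under the assumptions of step 3 with a true reduction of 35% and no smoke-free nights, a module passes in about 75–78% (mean), 74% (3 of 5) or 10% (all 5). Mean and 3 of 5 disagree in about 15%. The reading that stands apart is all 5, which nothing in the text suggests.

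**The case for a change.** The strongest case for a change is that both gaps feed a decision rule, that one of them favours a particular module, and that a sentence or two would close them before anyone sees data. Three parts of this stand. No readable passage gives either rule, the direction of any scoring effect would be fixed, and the mismatch between the End-of-Treatment text and Table 2 is real.

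The rest is weaker.

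- That the nightly diary carries the SMQ-R items is a fair inference from the design, but it is not stated. The text says only that the items can be adapted for momentary use.
- A practice quit of some hours leaves no smoke-free diary day, and the module describes gradual exposure.
- The required-field remark describes what the software permits. It does not say that the diary items are mandatory.
- A run of isolated zeros would show on a plotted series, which is where the analysis begins.

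Leaving smoke-free nights out is not clearly better than scoring them 0. It conditions on something that happens after treatment starts, and it penalises a module that works by removing smoking on the hardest nights. A night without smoking can reasonably count as no smoking for affect regulation. Leaving such nights out would also need a record of which they were. Table 2 lists the timeline follow-back only at baseline and end of treatment, so brief practice quits would be recalled over weeks, and the plan mentions no daily item asking whether the person smoked.

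**Conclusion.** No change to the plan follows. The count is a gap with an obvious filling: 3 of 5, as for abstinence, which fits a design built on replication across cases and a milestone judged across participants. Figure 3 may already settle it. The scoring of smoke-free nights is a trade-off between two defensible choices. Analysts can report the number of such nights by module and show whether the selected set depends on how they are scored.

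The size of any tilt is unknown and may be zero. It is nil if no practice period covers a diary day, and 4.5% to 13.6% in the nightly mean for 1 to 3 such nights per person. The larger simulated percentages illustrate a worst case and should not be read as expected bias. The Table 2 mismatch is clerical and is not shown to affect selection, which rests on change over the course of treatment. The conclusion assumes that the plotted series and non-overlap measures lead the judgment, as section 14.0 says, and that both milestones are applied.

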# 15.0 Data Monitoring Plan to Ensure the Safety of Participants:

In collaboration with [name] and co-mentors, [name] has developed a data safety and monitoring plan for this project that is commensurate with the with the risks, nature, size, and complexity of the study. The proposed study has been designated as a minimal risk study by the Rush University IRB, consists of a behavioral intervention only (no medication), and will occur at a single site. Further, pilot trial procedures have been updated to be conducted on a fully remote basis, with all study contacts occurring via phone or online assessment, to facilitate social distancing. Given these study characteristics, a Data Safety Monitoring Board will not be convened. As detailed below, data and safety monitoring for the pilot trial (i.e., Study 3 of the current project) will consist of oversight by the PI, in coordination with the Rush University Institutional

Review Board (IRB). The PI will be assisted by study Co-Investigator, [name], a board-certified Internal Medicine physician and Medical Director of the Rush University Prevention Center.

